16. STUDY ASSESSMENTS AND PROCEDURES

- **Pre-Treatment Period**

During the Pre-Treatment Period, subjects are consented and qualified (screened) for the study. Informed consent must be obtained before initiation of any clinical screening procedure that is

performed solely for the purpose of determining eligibility for this study. Evaluations performed as part of routine care before informed consent can be considered as screening evaluations if done within the defined screening period, and if permitted by the site's institutional review board (IRB)/ethics committee (EC) policies.

Study eligibility is based on meeting all of the study inclusion criteria and none of the exclusion criteria at screening and on Study Day 1 before study treatment administration. The following assessments will be conducted before subjects receiving their first dose of cabozantinib on this protocol:

- History and physical
- ECOG performance status
- Tumor measurement
- Blood analysis: CBC and differential, blood chemistries, blood or urine pregnancy test if appropriate
- Urine analysis, liver function tests
- Tumor biopsy (fresh biopsy if paraffin blocks are not available); If tumor blocks cannot be provided 20 unstained slides are requested; if 20 slides cannot be provided due to tumor sample size a minimum of 10 unstained slides are required;
- Blood sample for research purposes
- Radiology: CT scan of neck, chest, abdomen, pelvis

For each subject, the Pre-Treatment Period ends upon receipt of the first dose of study treatment or final determination that the subject is ineligible for the study.

○ **Treatment Period**

During the Treatment Period subjects will receive cabozantinib with pembrolizumab until either disease progression, the occurrence of unacceptable drug-related toxicity or for other reason(s) for subject withdrawal as described in Section 2.6. Subjects should be instructed to immediately inform the principal investigator (PI) of any AEs. Subjects experiencing dizziness, sleepiness, or other symptoms that could influence alertness or coordination should be advised not to drive or operate other heavy machinery.

The following schedule of assessments applies to all subjects

Table 5-1). More frequent assessments should be obtained if clinically indicated.

Table 16-1: Study Assessments

Test ^a	Study Treatment Period		Post-Treatment Period		
	Pre-therapy (Day -14 to 0)	Day 1 of each cycle (21 days) while on study drugs ⁿ	30 - 37 Days after last dose	At one year ^b	End of follow up at 2 years ^b
History and Physical	X	X	X (and every 3 months) ^b	X	X
Weight and ECOG PS	X	X	X (and every 3 months) ^b	X	X
Tumor Measurement	X ^a	X (every 9 weeks)		X ^m	
CBC and diff ^d	X	X ^c	X (and after 3 months)	X	X
Chemistries (Na, CL, CO2, K, BUN, blood glucose ^e Creatinine, Ca, Mg, Phos), Urine analysis	X	X ^{c,e}	X (and after 3 months)	X	X
Liver function panel ^f	X	X ^c	X (and every 3 months)	X	X
PT, PTT, INR	X	X ^c	X	X	
TSH	X	X ^c	X (and every 3 months)	X	X
12-lead ECG	X ^l	X ^l			
Tissue for Research Purposes (paraffin embedded) ^g	X				
Blood for Research Purposes	X ^k				
Toxicity Assessment ^h	X	X			
Radiology: CT-neck, chest, abdomen, and pelvis for tumor measurements ⁱ	X	X (every 9 weeks)		X	
Blood or Urine B-HCG ^j	X				

^a.a range of 4 days before or after the scheduled scans and screening tests is allowed – for scans , a 28 days period is allowed to obtain scans before initiation of therapy)

^b. Once the patient has fully recovered from the study drug-related toxicities or the patient enrolls in a hospice, the follow up can be done by a phone call if the patient is off the study drugs.

^cLaboratory testing will be performed every 3 weeks for the first 9 weeks followed by assessments every 6 weeks. CBC with diff, liver function panel and blood chemistries (excluding T3, T4, TSH, GGT, LDH, Amylase, Lipase; PT, PTT/INR) will continue to be done every 3 weeks with each new cycle following the first 9 weeks of therapy.

^d. CBC and diff includes: WBC, ANC, HCT, HGB, PLT, % lymphocytes, % monocytes, % neutrophils, other Differential (labs need to be done within 7 days of start of therapy)

^{sea}

^e. GGT, Amylase, Lipase, LDH can be performed every 3 cycles

^f. Liver function panel includes: Alk Phos, Total Bilirubin, SGOT (AST), SGPT (ALT), Total Protein.(Labs need to done within 7 days of start of therapy)

^g. If tumor paraffin blocks are not available, fresh biopsy will be obtained before the first treatment. If fresh biopsy is indicated, one core (or punch) will be collected in formalin and the second core (or punch) will be collected in liquid nitrogen. Optional end of treatment tumor biopsy (or at the time of progression) is allowed at Emory University and Moffitt Cancer Center. If fresh biopsy is indicated, one core (or punch) will be collected in formalin and the second core (or punch) will be collected in liquid nitrogen.

^h. **Toxicity assessment:** Common Toxicity Criteria (CTC) version 4.0 will be used. All toxicity grades (including grade 1) should be captured on the case report forms. All toxicities that occurred during treatment should be followed until resolution.

ⁱ **Tumor measurement:** The same type of scan should be used for repeat measurements. (CT, MRI or PET/CT are acceptable) ; A PET CT can be exchangeable with a CT scan for the purpose of tumor measurements ; A CT of the pelvis at screening can be omitted if a prior PET CT scan does not show pelvic involvement within 3 months from enrollment; CT scans (tumor measurements) during treatment (i.e. after baseline) should be obtained every 9 weeks from C1D1

^j **Pregnancy test** should be done in woman of child bearing age who are sexually active and may potentially be pregnant. Prior to study enrollment, women of childbearing potential (WOCBP) must be advised of the importance of avoiding pregnancy during trial participation and the potential risk factors for an unintentional pregnancy. In addition, men enrolled on this study should understand the risks to any sexual partner of childbearing potential and should practice an effective method of birth control. All WOCBP MUST have a negative pregnancy test within 7 days prior to first receiving investigational product. If the pregnancy test is positive, the patient must not receive investigational product and must not be enrolled in the study. In addition, all WOCBP should be instructed to contact the Investigator immediately if they suspect they might be pregnant (e.g., missed or late menstrual period) at any time during study participation.

^k **Blood for research before therapy**, 9 weeks into therapy, at 6 months, and end of treatment (or at the time of progression whichever is sooner).

^l **Screening EKG** in triplicate at eligibility. On treatment routine EKGs at each cycle for 3 cycles, and then every 9 weeks thereafter

^m Only for select patients who have lack of prior progression at one year

ⁿ- A 2 days window for infusion of Pembrolizumab is allowed for logistic reasons- Every effort should be made to avoid interruption in Cabozantinib administration as a result of changes in Pembrolizumab schedule. A 2 day window for clinical labs and history & physical is also allowed for logistical reasons.

If the subject is unable to have a study assessment taken within the defined time window due to an event outside of his or her control (eg, clinic closure, personal emergency, inclement weather, vacation), the assessment should be performed as close as possible to the required schedule.

Regular tumor assessments should be performed in accordance to the guidelines in Section o to determine if PD is present.

The Treatment Period ends when a subject receives his or her last dose of study treatment; the subject then enters the Post-Treatment Period.

○ **Post-Treatment and End on Treatment Period**

Subjects will return to the study site 30 to 37 days after their last dose of cabozantinib, pembrolizumab or both to complete end-of-study assessments.

At the end of 24 months of treatment on the combination of pembrolizumab and cabozantinib, patients who are in continued response and who in the opinion of the investigators can continue to benefit from therapy will be given the options of either terminating therapy, or continuing on the combination with the use of the EASE program overlooked by Exelixis ; This program will provide commercial cabozantinib to patients who wish to continue therapy for an additional 12 months of treatment; patients who continue on the EASE program will be followed as per standard of care at the respective institutions.

Laboratory and physical examinations will be performed. Remaining study treatment will be returned by the subject, and treatment compliance will be documented. Additional follow-up will occur for subjects with AEs related to study treatment that are ongoing at the time of this visit, and for subjects with SAEs related to study treatment that occur after the time of this visit.

○ Laboratory Assessments

Laboratory panels are composed of the following:

Hematology	
 • WBC count with differential (including at minimum: neutrophils, basophils, eosinophils, lymphocytes, monocytes) • hematocrit • platelet count • RBC count • hemoglobin • ESR • reticulocytes
Serum chemistry	
 • albumin • ALP • amylase • ALT • AST • bicarbonate • BUN • chloride • creatinine • GGT • Glucose • ionized calcium or total and corrected calcium • lactate dehydrogenase • lipase • magnesium • phosphorus • potassium • sodium • total bilirubin • total protein
Urinalysis	
 • appearance • color • pH • specific gravity • ketones • protein • UPCR • Glucose • bilirubin • nitrite • creatinine • urobilinogen • occult blood (microscopic examination of sediment will be performed only if the results of the urinalysis dipstick evaluation are positive)
Other	
 • TSH, Free T3 and T4 • Pregnancy test (urine or serum) for women of child-bearing potential • Blood for research studies • PT/INR or PTT • 24 hour urine collection for protein

ALP, alkaline phosphatase; ALT, alanine aminotransferase; AST, aspartate aminotransferase; BUN, blood urea nitrogen; ESR, erythrocyte sedimentation rate ; GGT, γ -glutamyltransferase; INR, International Normalized Ratio; PT, prothrombin time; PTT partial thromboplastin time; RBC, red blood cell; TSH, thyroid stimulating hormone; UPCR, urine protein/creatinine ratio; WBC, white blood cell.

Abnormalities in clinical laboratory tests that lead to a change in subject management (eg, dose delayed [withheld] or reduced, requirement for additional medication, treatment or monitoring)

are considered clinically significant for the purposes of this study, and will be recorded on the Adverse Events Case Report Form (CRF). If laboratory values constitute part of an event that meets criteria defining it as serious, the event (and associated laboratory values) must be reported as an SAE.

- **Tumor Assessment**

Response Criteria (RECIST 1.1)

For subjects who have measurable disease at baseline, this is a summary of overall response status calculation.

Evaluation of Target Lesions

Complete Response (CR): Disappearance of all target lesions

Partial Response (PR): At least a 30% decrease in the sum of the longest diameter (LD) of target lesions, taking as reference the baseline sum LD

Progressive Disease (PD): At least a 20% increase in the sum of the LD of target lesions, taking as reference the smallest sum of the LD recorded since the treatment started or the appearance of one or more new lesions

Stable Disease (SD): Neither sufficient shrinkage to qualify for PR nor sufficient increase to qualify for PD, taking as reference the smallest sum LD since the treatment started

Evaluation of Non-Target Lesions

Complete Response (CR): Disappearance of all non-target lesions and normalization of tumor marker level

Non-CR/Non-PD: Persistence of one or more non-target lesion(s) and/or maintenance of tumor marker level above the normal limits

Progressive Disease (PD): Appearance of one or more new lesions and/or unequivocal progression of existing non-target lesions

Although a clear progression of “non-target” lesions only is exceptional, the opinion of the treating physician should prevail in such circumstances, and the progression status should be confirmed at a later time by the review panel (or Principal Investigator).

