2.2 Study Design

2.2.1 Overview of Study Design

All patients will require measurable disease by RECIST 1.1 and will need documentation of disease progression after platinum based therapy; archival tissue will need to be submitted; if archival tissue is not possible a fresh biopsy is mandated.

Run-in phase:

Pembrolizumab will be initiated in Cycle 1 at the standard dose of 200 mg Q 3 weeks for one cycle.

A run in phase of cabozantinib at 40 mg/day will be performed for the first 6 patients, beginning in Cycle 1. If the combination is well tolerated (<2 DLTs in the first cycle), the trial will complete accrual at this dose level. If the combination is not well tolerated, with 2 DLTs in the first treatment cycle observed in the first 6 patients, the dose of cabozantinib will be decreased to 20 mg/day which will be the dose used for the rest of the study.

DLT Criteria

Adverse events (AEs) will be graded in accordance to the National Cancer Institute Common Terminology Criteria for Adverse Events (CTCAE) (v4.0). Dose-limiting toxicity (DLT) is defined as any of the following treatment-related AEs occurring during the DLT Evaluation Period, which will be during the first cycle of combined pembrolizumab and cabozantinib.

- Treatment-Related Non-Hematologic AEs:
 1. Any related \geq Grade 3 AE which is unexpected in severity and/or duration compared to the known safety profiles of cabozantinib and pembrolizumab when used as single agents, and that cannot be managed by dose modification (reduction or interruption) and adequate supportive care, and requires permanent discontinuation of cabozantinib and/or pembrolizumab.

2. Inability to take $\geq 75\%$ of the total planned cabozantinib dose for the DLT Evaluation Period because of a treatment-related AE leading to dose reductions and/or interruptions

For the AEs described in Section 3.3.2 - 3.3.2.19, the specific AE management guidelines in this section should be followed to determine the need for dose reductions and dose interruption.

- Treatment-Related Hematologic AEs:
 1. Grade 3 neutropenia of ≥ 7 days duration or any Grade 4 neutropenia
 2. \geq Grade 3 febrile neutropenia;
 3. All other hematologic toxicities of Grade 4 (except anemia as described in Section 3.3.2.4)

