When cabozantinib or pembrolizumab are discontinued for reasons deemed to be related to one or the other agent, the protocol calls for the discontinuation of both agents until and when the toxicities have reached a tolerable level (as specified in the dose modification sections) at which time both agents will be re-initiated. Patients who have interruption of both agents for more than 6 consequential weeks will be removed from the study; response assessment for these patients will still be assessed if available; in addition to assessment of OS and PFS based on the intent to treat analysis principle.	Assigned dose	First Dose Level Reduction
	40-mg cabozantinib oral qd	20-mg cabozantinib oral qd

Table 3-3: Dose Modifications of Cabozantinib for Treatment-Related AEs

CTCAE v.4.0 Grade	Recommended Guidelines for Management ^a
Grade 1 AEs	Add supportive care as indicated. Continue cabozantinib treatment at the current dose level if AE is manageable and tolerable.
Grade 2 AEs which are tolerable and are easily managed	Continue cabozantinib treatment at the current dose level with supportive care.
Grade 2 AEs which are intolerable and cannot be adequately managed	At the discretion of the investigator, cabozantinib should be dose reduced or interrupted. Note: It is recommended that dose holds be as brief as possible.
Grade 3 AEs (except clinically non-relevant laboratory abnormalities)	Cabozantinib should be interrupted unless the toxicity can be easily managed with a dose reduction and optimal medical care. Note: It is recommended that dose holds be as brief as possible.
Grade 4 AEs (except clinically non-relevant laboratory abnormalities)	Subjects should have cabozantinib interrupted immediately. Discontinue cabozantinib unless the following criteria are met: 
• Subject is deriving clear clinical benefit as determined by the investigator and agreed by the Sponsor• Toxicity can be managed with a dose reduction following recovery to Grade 1 (or baseline) and optimal medical care

AE, adverse event.

Note: The dose delay and modification criteria for specific medical conditions are provided in Section 3.3.2. For re-treatment criteria of study treatment after a dose hold see Section 3.3.1.1.

^a Study treatment dose adjustment is only needed if the toxicity was deemed related to cabozantinib treatment or had an unclear relationship to cabozantinib treatment.

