All laboratory data required by this protocol and any other clinical investigations should be reviewed. Any abnormal value that leads to a change in subject management (eg, dose reduction or delay or requirement for additional medication or monitoring) or that is considered to be of clinical significance by the investigator should be reported as an AE or SAE as appropriate.

- **Pregnancy**

If a subject becomes pregnant during the study, she will be taken off study treatment and will be followed through the end of her pregnancy. The investigator must inform the Sponsor of the pregnancy. Forms for reporting pregnancies will be provided to the study sites upon request. The outcome of a pregnancy (for a subject or for the partner of a subject) and the medical condition of any resultant offspring must be reported to Exelixis or designee. Any birth defect or congenital anomaly must be reported as an SAE, and any other untoward events occurring during the pregnancy must be reported as AEs or SAEs, as appropriate.

- **Medication Errors/Overdose**

Any study drug administration error or overdose that results in an AE, even if it does not meet the definition of serious, requires reporting within 24 hours to Exelixis or designee.

- **Follow-Up of Adverse Events**

Any related SAEs or any AEs assessed as related that led to treatment discontinuation, including clinically significant abnormal laboratory values that meet these criteria, ongoing 30 days after the decision to discontinue study treatment must be followed until either resolution of the event or determination by the investigator that the event has become stable or irreversible. This follow-up guidance also applies to related SAEs that occur *> 30 days after the decision to discontinue* study treatment. The status of all other continuing AEs will be documented as of 30 days after the decision to discontinue study treatment.

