when CRFs are illegible or when errors in data transcription are suspected. In case of special problems or governmental queries or requests for audit inspections, it is also necessary to have access to the complete study records, provided that subject confidentiality is protected.

- **Audits and Inspections**

The investigator should understand that source documents for this study should be made available, after appropriate notification, to qualified personnel from the Exelixis Quality Assurance Unit (or designee) or to health authority inspectors. The verification of the CRF data must be by direct inspection of source documents.

- **Case Report Forms**

For enrolled subjects, all and only data from the procedures and assessments specified in this protocol and required by the CRFs should be entered on the appropriate CRF. Data from some procedures required by the protocol, such as physical examinations and laboratory results, will be recorded only on the source documents and will not be transcribed to CRFs. Additional procedures and assessments may be performed as part of the investigator's institution or medical practice standard of care and may not be required for CRF entry.

For each subject enrolled, the CRF (paper or electronic) must be completed and signed by the PI or authorized delegate from the study staff.

All paper forms should be typed or filled out using indelible ink and must be legible. Errors should be crossed out but not obliterated, the correction inserted, and the change initialed and dated by the investigator or his or her authorized delegate.

The investigator should ensure the accuracy, completeness, legibility, and timeliness of the data in the CRFs and in all required reports.

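### The rules for recording laboratory toxicities conflict, and because safety is analyzed only from CRF adverse-event terms, laboratory toxicity can be under-counted

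*Combined protocol and SAP*

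**What the plan says.** Five places in the combined protocol and SAP bear on whether a laboratory abnormality reaches the study database.

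- **Table 16-1, footnote h (toxicity assessment):** "All toxicity grades (including grade 1) should be captured on the case report forms".
- **Section 16, Laboratory Assessments:** the AE form receives "Abnormalities in clinical laboratory tests that lead to a change in subject management". Management change is illustrated broadly: a withheld or reduced dose, or a need for extra medication, treatment or monitoring.
- **Section 17, Laboratory Data:** "Any abnormal value that leads to a change in subject management" is covered, and so is a value "or that is considered to be of clinical significance by the investigator should be reported as an AE or SAE as appropriate".
- **Section 17, Adverse Events:** the AE definition includes abnormal laboratory findings. A later sentence in the same subsection makes recording them as AEs conditional on criteria said to be in Section 3.3.
- **Section 25, Case Report Forms:** data from some procedures, including "laboratory results, will be recorded only on the source documents and will not be transcribed to CRFs".

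Section 18 then bases the safety assessment on AEs, using the terms entered on the CRFs. It plans no table of laboratory grades from measured values.

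**The concern.** Toxicity is a stated objective twice over: safety and tolerability is the run-in primary objective in the synopsis, and further definition of toxicities is a secondary objective in Section 2.1. If laboratory events enter the database according to whether someone acted on them, the reported rate measures action or judgment, not how often a CTCAE grade occurred. Section 3.3.2 lists many laboratory AEs seen in at least 5% of cabozantinib-treated subjects, including neutropenia, thrombocytopenia, leukopenia and raised lipase, AST and ALT, so this is not a marginal class of event.

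The run-in adds a further reason for a clear rule. Section 2.2.1 defines some DLTs by hematologic grade, for example "All other hematologic toxicities of Grade 4 (except anemia as described in Section 3.3.2.4", without reference to a management change. A recording rule tied to management is narrower than that definition, and two DLTs in the first six patients change the decision.

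**Working it through.** The documents state no laboratory toxicity rate or capture rate for this trial, so there is no figure to reproduce. The check is to follow one event through the text: a Grade 3 or 4 laboratory toxicity for which nobody changes a dose, adds a drug or adds monitoring, and which the investigator judges non-relevant.

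| Place | Does it put the event in the database? |
|---|---|
| Table 16-1, footnote h | Yes, whatever the grade |
| Section 16, Laboratory Assessments | Not triggered: no management change |
| Section 17, Laboratory Data | Not triggered: no management change, not judged significant |
| Section 17, Adverse Events | Unclear: depends on Section 3.3, which gives dose-modification guidance and no laboratory recording criteria |
| Section 25, Case Report Forms | No: results stay in source documents |
| Section 18, Safety Analysis | Uses only what is on the CRF as an AE |

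A site working from footnote h records the event. A site working from Sections 16, 17 and 25 need not, and no sentence ranks the rules.

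The protocol does expect such values. Table 3-3 labels its Grade 4 row "Grade 4 AEs (except clinically non-relevant laboratory abnormalities"), and the Grade 3 row carries the same exception.

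Possible backstops:

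1. Section 20 says in general terms that OnCore records all study-related information. Section 25 is the specific statement, and it excludes laboratory results.
2. Section 3.3.2.4 sends some results to a laboratory data vendor, but only additional or more frequent tests in subjects with hematologic toxicity. No analysis uses them.
3. Section 21 has the DSMC monitors review about 10% of charts, for Emory patients only.
4. Section 26 provides calls, spreadsheets and OnCore reviews, but no requirement to grade every laboratory value.

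**Size, as illustration only.** Let p be the true proportion of patients with a Grade 3-4 laboratory toxicity and c the fraction recorded. Expected recorded patients = 34 × p × c. Both p and c are assumed, and 34 is the planned number of evaluable subjects.

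| p | c = 1 | c = 0.9 | c = 0.7 | c = 0.5 |
|---|---|---|---|---|
| 0.10 | 3.4 | 3.1 | 2.4 | 1.7 |
| 0.20 | 6.8 | 6.1 | 4.8 | 3.4 |
| 0.30 | 10.2 | 9.2 | 7.1 | 5.1 |

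For example, 34 × 0.20 × 0.7 = 4.76, against 34 × 0.20 = 6.8 with full capture. Since c cannot exceed 1, the recorded count can equal the true count or fall below it.

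**The case against.** Several points on the other side stand.

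- No single sentence says laboratory abnormalities are recorded *only* if they change management. Sections 16 and 17 each give a sufficient trigger, and the limit comes from reading them together with the Section 3.3 pointer.
- The trigger is wide. Added medication or monitoring counts, and the protocol itself calls for such steps for raised transaminases or bilirubin (3.3.2.3), proteinuria (3.3.2.10) and hypophosphatemia (3.3.2.12). Many Grade 3-4 values would be recorded even on the narrow reading.
- Table 3-3 governs dosing and says nothing about recording. It shows that values judged non-relevant are anticipated, not that they are dropped.
- Section 25 concerns transcription of raw results. Entering a graded toxicity on the AE form is a different act, so Section 25 and footnote h can both be obeyed. But Section 25 does remove the laboratory values that could have shown a missing AE.
- Differences between the two sites are a possibility. Section 26 monitoring could reduce them.

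Two stronger readings are tempting. A reader might infer that the run-in will miss a DLT, perhaps by applying the pembrolizumab Grade 3/4 lymphocytopenia rate of 9% in Section 3.4.1 to six patients. The documents do not support this. That rate combines Grades 3 and 4, while the criterion that could apply to lymphocytopenia is Grade 4. It carries no time window, while DLTs are assessed over one cycle, and the listed incidences include unapproved regimens. DLTs are defined as treatment-related AEs, nothing requires them to be counted from the CRF, and investigators can identify them from source results or raise them on the weekly calls.

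A reader might also use the hyponatremia and hypoalbuminemia rates in Section 3.4.1 as evidence of lost severe events. Those rates have no Grade 3/4 split, and the documents do not say how often such findings prompt no action.

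**Conclusion.** The conflict is real and unresolved in the text. Taken with the exclusion of laboratory results from the CRF and an AE-only safety analysis, it means laboratory toxicity **can** be under-counted. Whether it **is** depends on which rule sites follow and on investigator judgment. The exposed events are Grade 3-4 toxicities that prompt no action and are judged non-relevant, and a larger share of Grades 1-2.

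The size cannot be derived from the documents; the direction can, and it is downward only. A missed hematologic DLT is possible but not shown. The point merits a clarifying amendment because it affects a stated objective and is inexpensive to correct.

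**What to change.** Reconcile footnote h of Table 16-1, Section 16 (Laboratory Assessments), Section 17 (Adverse Events and Laboratory Data) and Section 25 (Case Report Forms) into one rule consistent with footnote h:

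1. Record on the AE CRF every treatment-emergent laboratory abnormality of CTCAE v4.0 Grade 3 or higher, and every hematologic toxicity meeting a Section 2.2.1 DLT criterion, whether or not management changed. Replace the Section 3.3 pointer in Section 17 with this rule.
2. Amend Section 25 so that the scheduled CBC, chemistry, liver and thyroid results are entered in OnCore.
3. Add to Section 18 a table of worst CTCAE grade per laboratory parameter in the safety population. This covers the lower grades that footnote h asks for without a separate AE entry for each.

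The cost is data entry for every treated patient. That may be somewhat more than 34, because Section 18 counts 34 evaluable subjects, evaluability requires a follow-up scan, and run-in subjects can be replaced. Full panels over repeated cycles are a real workload, though a bounded one. Reported laboratory toxicity rates may look less favorable. No new tests are needed and no dosing rule changes.
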